**Table I4 Dose Reduction for Osimertinib to Manage Adverse Events**

	Starting osimertinib dose CCI
Reduced dose -1	CCI

On resolution of toxicity within 3 weeks:

- If an AE subsequently requires dose interruption, osimertinib may restart at the same dose or the reduced dose, on resolution/improvement of the AE at the discretion of the investigator.

### **I 2.1 ILD/Pneumonitis-like Toxicity**

If new or worsening pulmonary symptoms (eg, dyspnoea) or radiological abnormality suggestive of ILD is observed, an interruption in osimertinib dosing is recommended, and the AstraZeneca study team should be informed. It is strongly recommended to perform a full diagnostic workup, to exclude alternative causes such as lymphangitic carcinomatosis, infection, allergy, cardiogenic oedema or pulmonary haemorrhage. The results of full diagnostic workup (including high resolution CT, blood and sputum culture, haematological parameters) will be captured by eCRF. All image data should be provided to AstraZeneca. In the presence of confirmatory high resolution CT scans where other causes of respiratory symptoms have been excluded, a diagnosis of ILD should be considered and osimertinib permanently discontinued.

### **I 2.2 Keratitis**

Patients presenting with signs and symptoms suggestive of keratitis such as acute or worsening: eye inflammation, lacrimation, light sensitivity, blurred vision, eye pain and/or red eye should be referred promptly to an ophthalmology specialist.

### **I 2.3 Changes in Cardiac Contractility**

Based on the available clinical study data, a causal relationship between effects on changes in cardiac contractility and osimertinib has not been established. In patients with cardiac risk factors and those with conditions that can affect LVEF, cardiac monitoring, including an assessment of LVEF at baseline and during treatment, should be considered. In patients who develop relevant cardiac signs/symptoms during treatment, cardiac monitoring including LVEF assessment should be considered.

### I 3 Savolitinib Dose Modification and Guidance

#### I 3.1 Savolitinib Dose Modification and Guidance

Substantial acute toxicities should be managed as medically indicated and with temporary suspension of savolitinib, as appropriate unless due to suspected hypersensitivity (see Section I 3.3).

Dose reductions or holds are allowed as clinically indicated by the treating physician and in line with Table I5 and Table I1. For each patient, a maximum of 2 dose reductions of savolitinib will be allowed. No dose re-escalations are allowed. Guidance on dose level reduction is presented in Table I5.

**Table I5 Dose Reduction for Savolitinib Adverse Events**

	Starting savolitinib dose CCI
Reduced dose -1	CCI
Reduced dose -2	CCI

Note: Only 2 dose reductions of savolitinib are permitted.

#### I 3.2 Hepatotoxicity Management Guideline

- Promptly evaluate patients with elevated LFTs during treatment with savolitinib for alternative aetiologies and PHL criteria, and discontinue potential contributing concomitant medications or alternative causal agents, as well as anti-coagulants, if appropriate.
- Ensure a PK sample is collected as soon as feasible when the patient discontinues due to an AE reaction (see Table 1, Table 2 and Section 8.5).
- If a patient discontinues due to LFT abnormality, LFT monitoring should continue until resolved to Grade 1 or baseline or an apparent plateau has been reached.

##### I 3.2.1 Dose Modification Due to Drug-related Hepatotoxicity

- Discontinue drug if:
  - ALT or AST > 8 × ULN with TBL elevation above baseline or ULN, or
  - ALT or AST > 5 × ULN for up to one week (< 7 days) with TBL elevation above baseline or ULN, following immediate withholding of drug. Repeat LFT testing within 2 to 3 days and at least twice a week until improvement to Grade 1 or baseline.
  - ALT or AST > 3 × ULN and (TBL > 2 × ULN or INR > 1.5 if not on anticoagulants that elevate the INR), or

- AST or ALT > 3 × ULN with the appearance of fatigue, nausea, vomiting, right upper quadrant pain or tenderness, fever, rash and/or eosinophilia > 5%
- Withhold dosing if ALT or AST > 5 × ULN for > 2 weeks or 8 × ULN without TBL elevation above baseline or ULN, repeat LFT testing twice a week for one week:
  - If improved to Grade 1 or baseline in one week, resume at reduced dose with LFT testing twice a week for 6 weeks
  - If not, discontinue
- Withhold dosing if ALT or AST > 3 × ULN and concurrent TBL > 1.5 × ULN, repeat LFT testing twice a week for one week:
  - If both ALT/AST and TBL improved to Grade 1 or baseline in one week, resume at reduced dose with LFT testing twice a week for 6 weeks
  - If not, discontinue
- Withhold dosing if ALT or AST > 3 × ULN and concurrent TBL > 1 × ULN to 1.5 × ULN, repeat LFT testing twice a week for one week,
  - If both ALT/AST and TBL improved to normal range (< Grade 1) or baseline in one week, resume at same dose with LFT testing twice a week for 6 weeks
  - If not, resume at reduced dose
- Continue dosing if ALT or AST > 3 × ULN without TBL elevation above baseline or ULN, repeat LFT testing every week
  - If ALT or AST trending upward, withhold dosing and repeat LFT twice a week for one week
  - If improve to Grade 1 or baseline in one week, resume at same dose with LFT testing every week for 6 weeks
  - If improve to Grade 1 or baseline in 2 weeks, resume at reduced dose with LFT testing every week for 6 weeks
  - If not, discontinue
- Discontinue for recurrent ALT or AST > 5 × ULN
- Discontinue for recurrent ALT or AST > 3 × ULN and TBL > 1.5 × ULN
- Withhold dosing for recurrent ALT or AST > 3 × ULN without TBL elevation above baseline or ULN, repeat LFT testing twice a week for one week
  - If improve to Grade 1 or baseline in one week, resume at reduced dose with LFT testing every week for 6 weeks; if not, discontinue

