### Type of Patient and Disease Characteristics

- 4 Histologically or cytologically confirmed locally advanced or metastatic EGFRm+ NSCLC harbouring an EGFR mutation known to be associated with EGFR-TKI sensitivity and that is permitted in the osimertinib national label (such as exon 19 deletion and/or L858R), which is not amenable to curative therapy.
- 5 Documented radiologic PD following treatment with osimertinib (osimertinib does not need to be the most recent therapy).
- 6 Have MET amplification as determined by central MET FISH testing on tumour specimen collected following progression on prior osimertinib treatment.
- 7 Available FFPE tumour specimen for central MET FISH analysis or willingness to collect an additional specimen for central testing, which fulfils the following requirements:
  - Obtained following progression on previous osimertinib therapy.
  - Obtained within 2 years of submission for MET analysis.
  - Sufficient specimen to meet the minimum specimen requirement defined in the current Laboratory Manual.
- 8 At least one lesion, not previously irradiated, not biopsied during the screening period, that can be accurately measured at baseline as  $\geq 10$  mm in the longest diameter (except lymph nodes which must have short axis  $\geq 15$  mm) with CT or MRI, which is suitable for accurate repeated measurements. If only one measurable lesion exists, it is acceptable to

- be used as long as baseline tumour assessment scans are done at least 14 days after the screening tumour specimen collection is performed.
- 9 Patients must have received at least one but no more than 3 prior lines of therapy (including investigational therapy) in the locally advanced/metastatic setting.
    - No more than one prior line of chemotherapy regimen is acceptable.
    - A chemotherapy regimen including a programmed cell death-1 or a programmed cell death ligand-1 agent is acceptable, provided it was not the most recent line of therapy.
    - No more than 2 prior lines of therapy containing EGFR-TKI are acceptable.
  - 10 Adequate haematological function defined as:
    - Absolute neutrophil count  $\geq 1500/\mu\text{L}$
    - Haemoglobin  $\geq 9$  g/dL (no transfusion in the past 2 weeks)
    - Platelets  $\geq 100000/\mu\text{L}$  (no transfusion in the past 10 days)
  - 11 Adequate liver function defined as:
    - ALT and AST  $\leq 2.5 \times$  the ULN with TBL  $\leq$  ULNOR

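### Appendix I 3.2.1: the liver dose-modification limbs conflict for certain ALT/AST and bilirubin combinations (upper-only duration bound, missing recurrence limb, undefined bilirubin reference)

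*Supplement*

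**What the plan says.** Appendix I 3.2.1 of the protocol (Amendment 2) gives the savolitinib actions for drug-related hepatotoxicity as a list. The limbs that matter here, with labels used below, are:

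- **A, discontinue:** "ALT or AST > 8 × ULN with TBL elevation above baseline or ULN"; no duration condition.
- **B, discontinue:** ALT/AST above 5 × ULN "for up to one week (< 7 days) with TBL elevation above baseline or ULN, following immediate withholding of drug".
- **C, discontinue:** "ALT or AST > 3 × ULN and (TBL > 2 × ULN or INR > 1.5 if not on anticoagulants" that raise the INR; no duration condition.
- **D, withhold:** "Withhold dosing if ALT or AST > 5 × ULN for > 2 weeks or 8 × ULN without TBL elevation" above baseline or ULN. If improved in one week, resume at a reduced dose; otherwise discontinue.
- **E, withhold:** "Withhold dosing if ALT or AST > 3 × ULN and concurrent TBL > 1.5 × ULN". If improved in one week, resume at a reduced dose; otherwise discontinue.
- **F, withhold:** "Withhold dosing if ALT or AST > 3 × ULN and concurrent TBL > 1 × ULN to 1.5 × ULN". If normalised or back to baseline in one week, resume at the same dose; otherwise resume at a reduced dose.
- **G, continue:** ALT/AST above 3 × ULN "without TBL elevation above baseline or ULN, repeat LFT testing every week".

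A separate limb discontinues for ALT/AST above 3 × ULN with listed symptoms or eosinophilia.

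Three limbs deal with recurrence. Recurrent ALT/AST above 5 × ULN: discontinue. Recurrent above 3 × ULN with TBL above 1.5 × ULN: discontinue. Recurrent above 3 × ULN without a TBL rise: withhold, then resume at a reduced dose or discontinue.

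Inclusion criterion 11 (Section 5.1, "Adequate liver function defined as") admits TBL above ULN up to 1.5 × ULN if ALT and AST are within normal. The Amendment 2 summary says that text was added to I 3.2.1 about discontinuing when drug is already being withheld.

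**The concern.** Limb B is the only discontinue limb with a duration condition, and that condition is a maximum. Its counterpart without a TBL rise, limb D, uses a minimum. Read as written, an episode can leave the discontinue limb by lasting longer. The recurrence limbs skip one bilirubin band. The phrase about TBL above baseline or ULN can be read in two ways that lead to different actions.

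Savolitinib is given in both arms. Table 3 reports hepatotoxicity in 35.0% of patients in the savolitinib database, with 11.5% at Grade 3 or above. Where the limbs disagree, two sites following the same page can act differently on the same result. That is first a matter of consistent patient safety. It also bears on the rate of discontinuation due to adverse events, a stated safety endpoint, although safety is only summarised descriptively.

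**Working it through.** The plan states no figure to reproduce, so the check applies the limbs literally.

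**Set-up.** First episode, no symptoms, INR at most 1.5, baseline TBL within normal. ALT/AST in 3 bands (>3–5, >5–8, >8 × ULN), TBL in 5 bands (≤ baseline; > baseline but ≤ ULN; >1–1.5; >1.5–2; >2 × ULN) and duration in 3 bands (<7 days, 7–14 days, >14 days) give 3 × 5 × 3 = 45 combinations. The bilirubin phrase is read first as either threshold exceeded, then as the higher of the two exceeded.

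**Step 1: duration.** Limbs met at ALT/AST >5–8 × ULN:

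| TBL | <7 days | 7 days or more |
|---|---|---|
| >1–1.5 × ULN | B discontinue and F withhold | F withhold only |
| >1.5–2 × ULN | B discontinue and E withhold | E withhold only |
| >2 × ULN | B and C discontinue, E withhold | C discontinue, E withhold |

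These rows are the same on both readings, because TBL exceeds both baseline and ULN. In the first two rows a discontinue limb is lost at day 7. In the first row what remains never ends in discontinuation.

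A side-by-side case: ALT/AST 6 × ULN for 20 days, withheld, unimproved after a week. Without a TBL rise, limb D ends in discontinuation (the conditions of G are met as well). With TBL 1.3 × ULN, only F applies, and dosing resumes at a reduced dose.

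**Step 2: the week read as an observation window.** Suppose the amendment meant up to a week of observation after withholding. For TBL >1.5–2 × ULN unimproved after a week, B and E then both end in discontinuation and agree. For TBL >1–1.5 × ULN unimproved after a week, B says discontinue and F says resume at a reduced dose. The conflict remains, and no ranking is given.

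**Step 3: recurrence.** Take recurrent ALT/AST 4 × ULN with TBL 1.3 × ULN and normal baseline. The first recurrence limb needs ALT/AST above 5, the second needs TBL above 1.5, and the third needs no TBL rise. None is met. Only F applies, which can resume at the same dose and never discontinues. The same recurrence without a TBL rise goes to the third limb: reduced dose or discontinue.

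**Step 4: the bilirubin reference.**

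- *Either threshold.* With TBL above baseline but ≤ ULN, ALT/AST >3–5 × ULN meets no limb at any of the 3 durations, and >5–8 × ULN meets none at 7–14 or >14 days. That is 3 + 2 = 5 of 45 combinations without a limb.
- *Higher of the two.* The same results count as no rise and fall to G (and D where it applies): 0 of 45 are empty. But take a baseline TBL of 1.4 × ULN, allowed by criterion 11, and a current TBL of 1.2 × ULN, with ALT/AST >3–5 × ULN. F is met (TBL >1–1.5 × ULN) and so is G (no rise above 1.4): withhold and continue together.

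**Step 5: is the action stated elsewhere?** Table I1 excludes toxicities with their own guideline. The hepatic row of Table I2 refers back to I 3.2. Appendix E says it is not a comprehensive management guide, and its potential Hy's Law definition needs TBL of at least 2 × ULN. None of these supplies the missing dose action.

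**The case against.** The strongest reply is that an episode followed from onset passes through the first 7 days before it can reach day 7, so limb B will already have applied. This largely stands for closely monitored patients. The routes left are an elevation of uncertain onset, which is plausible because scheduled liver tests fall once per 28-day cycle after week 10, and a TBL rise a week or more after ALT/AST passed 5 × ULN. Limb B does not say whether its days are counted for ALT/AST alone or for the combination. In any case the unranked overlap inside the first 7 days is untouched by this reply.

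Second, the week may be an observation window, as the amendment summary may suggest. The sentence itself does not say so, and Step 2 shows a conflict even then.

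Third, sites are not without support. Appendix E requires review without delay and notification from ALT or AST of 3 × ULN, I 3.2 requires prompt evaluation, Section 6.6 provides for discussion with the sponsor, and I 3.1 allows holds as clinically indicated. This stands, but these provisions route the case to judgement and name no action.

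Fourth, same-dose resumption under F needs a stricter recovery (normal range or baseline) than the recurrence limb, and I 3.3 restricts restarts after interruptions for savolitinib-related general toxicities in the first 6 weeks. Both soften the recurrence point. Neither supplies a recurrence limb, and the I 3.3 restriction for general toxicities covers only early interruptions.

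A reader might infer that longer elevations are generally treated less strictly. The list does not support that: a discontinue limb is met at every duration for ALT/AST above 8 × ULN with a TBL rise, TBL above 2 × ULN, INR above 1.5, symptoms, and recurrent ALT/AST above 5 × ULN. A reader might also infer that common results have no rule at all. The empty combinations exist only on the either-threshold reading, and nothing in the documents says how often they occur. The Table 3 rates are for hepatotoxicity overall.

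**Conclusion.** The point holds in a limited form. Limbs in I 3.2.1 contradict each other or leave a case uncovered in three places:

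1. ALT/AST >5–8 × ULN with TBL >1–2 × ULN, through the upper-only duration bound and the absence of precedence.
2. Recurrent ALT/AST >3–5 × ULN with TBL >1–1.5 × ULN, through the missing recurrence limb.
3. Results that turn on the undefined bilirubin reference: 5 of 45 combinations without a limb on one reading, or withhold and continue together for some patients with raised baseline TBL on the other.

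Item 1 does not depend on how the bilirubin phrase is read when baseline TBL is normal. Item 2 assumes a normal baseline. The grid assumes a first, asymptomatic episode with INR at most 1.5. No share of patients can be attached to any of the three. This is a patient-safety inconsistency that should be mended. It does not threaten the efficacy analysis, and no view is taken here on which clinical action is right.

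**What to change.** The sponsor should reconcile the I 3.2.1 limbs so that every ALT/AST, TBL and episode combination has one stated action. That means four changes:

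- Say what the duration in limb B measures, from when it is counted, and whether it is a condition for the limb or an observation period during withholding.
- Define the bilirubin reference once, including for patients who enter with raised TBL, and use it in every limb.
- State which limb takes precedence where two are met.
- Cover recurrent ALT/AST >3–5 × ULN with TBL >1–1.5 × ULN.

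Setting the list out as a single grid would expose any remaining gap. Which action belongs in each cell is for the sponsor's clinicians.

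The cost is rewriting one page of the appendix, with no new tests or visits. It would go into an amendment needing the usual ethics and regulatory approvals; the sponsor classed its previous change to this section as substantial.

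### In Appendix I 3.2.1, overlapping liver-test bullets with no stated precedence let the same ALT/AST and TBL values meet two instructions with different outcomes

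*Supplement*

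**What the plan says.** Appendix I 3.2.1 is a list of bullets. The ones that matter here are as follows.

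**Discontinue**
- D1: "ALT or AST > 8 × ULN with TBL elevation above baseline or ULN".
- D2: "ALT or AST > 5 × ULN for up to one week (< 7 days) with TBL elevation above baseline or ULN, following immediate withholding of" the drug.
- D3: "ALT or AST > 3 × ULN and (TBL > 2 × ULN or INR > 1.5 if not on anticoagulants that elevate the INR), or" (a symptom criterion follows).

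**Withhold**
- W1: "Withhold dosing if ALT or AST > 5 × ULN for > 2 weeks or 8 × ULN without TBL elevation above baseline or ULN". Recovery within one week leads to a reduced dose; otherwise discontinue.
- W2: "Withhold dosing if ALT or AST > 3 × ULN and concurrent TBL > 1.5 × ULN". Recovery of both tests within one week leads to a reduced dose; otherwise discontinue.
- W3: "Withhold dosing if ALT or AST > 3 × ULN and concurrent TBL > 1 × ULN to 1.5 × ULN". Recovery within one week leads to the same dose; otherwise dosing resumes at a reduced dose. This bullet has no discontinuation branch.

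**Continue**
- C: "Continue dosing if ALT or AST > 3 × ULN without TBL elevation above baseline or ULN". Dosing is withheld only if values trend upward. Recovery in one week then leads to the same dose, recovery in two weeks to a reduced dose, and otherwise discontinuation.

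**Recurrent events**
- R1: discontinue for recurrent ALT/AST above 5 × ULN, with no condition on TBL.
- R3: withhold for recurrent ALT/AST above 3 × ULN without TBL elevation, with resumption at a reduced dose if recovered in one week.

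The section does not say which bullet prevails when two are met. In Table I2, the hepatic entry for savolitinib refers back to I 3.2.

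**The concern.** W1, W2, W3, C and R3 have no upper ALT/AST limit, and W2 also has no upper TBL limit. Their ranges therefore run into those of D1, D3 and R1, and W1 runs into C. Two sites that both follow the text can reach different outcomes for the same patient.

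For patients, this is an ambiguity in a liver-safety rule. Table 3 (Section 2.3.1) cites specific dose-modification guidance as part of the mitigation for hepatotoxicity. Recruitment has ended, but Sections 4.1.4 and 6.7 provide for new cross-overs and for treatment beyond the final data cut-off, so the rule remains in use.

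For the data, the discontinuation rate due to AEs is a named safety endpoint (Table 4). Section 9.4.3 also tabulates AEs leading to interruption and dose reduction. These figures would depend partly on which bullet a site follows.

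**Working it through.** The plan gives no figure to reproduce. The check takes the bullets as written and looks for values that satisfy two of them.

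**Overlaps by range (multiples of ULN)**

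(a) ALT/AST > 8. With TBL > 1 to 1.5, D1 and W3 both hold: discontinue, against withhold and then resume, at a reduced dose even if not improved. With TBL > 1.5, D1 and W2 both hold: discontinue, against withhold with possible resumption.

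(b) ALT/AST > 3 with TBL > 2. D3 and W2 both hold, because TBL above 2 is also above 1.5: discontinue, against withhold with possible resumption.

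(c) ALT/AST at the 8 threshold or above, or > 5 for more than 2 weeks, without TBL elevation. W1 and C both hold: withhold, against continue. Resumption terms differ even if C's upward-trend clause leads to a hold. Recovery in one week gives a reduced dose under W1 and the same dose under C. Recovery only by two weeks gives discontinuation under W1 and a reduced dose under C.

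(d) Recurrent ALT/AST > 5 without TBL elevation. R1 and R3 both hold: discontinue, against withhold with possible resumption.

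**Illustrative grid**

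The grid takes ALT/AST 4, 6, 9 and TBL 0.9, 1.3, 1.8, 2.5 × ULN, so 3 × 4 = 12 cells. It assumes a first event, no symptoms, normal INR, baseline TBL within ULN, and an elevation not lasting more than 2 weeks. D2 is in brackets because it applies after a hold.

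| ALT/AST | TBL 0.9 | TBL 1.3 | TBL 1.8 | TBL 2.5 |
|---|---|---|---|---|
| 4 | C | W3 | W2 | D3, W2 |
| 6 | C | W3 [D2] | W2 [D2] | D3, W2 [D2] |
| 9 | W1, C | D1, W3 [D2] | D1, W2 [D2] | D1, D3, W2 [D2] |

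- Without D2, the rows give 1 + 1 + 4 = 6 overlapping cells of 12: 5 discontinue against withhold, and 1 withhold against continue.
- With D2, ALT 6 at TBL 1.3 and 1.8 are added: 6 + 2 = 8 of 12, of which 7 are discontinue against withhold.
- If the elevation lasts 3 weeks, ALT 6 at TBL 0.9 also meets W1 and C, and D2 no longer applies: 6 + 1 = 7 of 12.
- Over a short and a 3-week duration together, the count is 6 + 7 = 13 of 24 without D2, and 8 + 7 = 15 of 24 with it.

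Not every value conflicts. At first occurrence, ALT 4 with TBL 1.3 or 1.8 meets one bullet only.

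**The case against.** **Discontinue may be meant to prevail.** The bullets run roughly from severe to mild, Table I2 concerns permanent discontinuation and points to I 3.2, and the note to Table I1 sends such events to Table I2. A sensible reader could let the discontinue bullets win. This is plausible, but no sentence says it. It would also leave ALT 9 without TBL elevation unresolved: 1 cell of 12, or 3 of the 24 two-duration cells.

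**The actions are not opposite on day one.** Discontinue and withhold both stop dosing at once. This stands: in (a), (b) and (d) the conflict is about resumption. In (c), entry required ALT/AST no higher than 2.5 × ULN (Section 5.1, criterion 11) and liver tests are weekly for the first 10 weeks, so a patient at 9 × ULN has usually trended upward and C would also withhold. That narrows (c), but the resumption terms still differ.

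**D2 is a later step, not a rival instruction.** It follows a hold, and the Amendment 2 summary of changes describes the added instruction in that sense. This stands, so the lower count of 6 leads here.

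**Other safeguards exist.** A case such as ALT 4 with TBL 2.5 × ULN meets the potential Hy's Law criteria in Appendix E, which bring SAE reporting and contact with the Study Physician. Section 6.6 allows discussion of dose changes with the sponsor. These lower the chance of unnoticed divergence. However, Appendix E disclaims being a full management guide and does not reach the cases with TBL 1.3 × ULN or normal TBL. The statement in I 3.3 that recommendations are guidelines only is confined to hypersensitivity management and pre-treatment.

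**Conclusion.** The contradiction is real but limited to ranges (a) to (d). It rests on the literal text and on the absence of any stated precedence. The overlaps do not depend on the grid, although the counts (6 of 12, or 8 of 12 with D2) do.

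A reader might infer more than the documents support, in four ways:

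- *That every bullet is open-ended.* It is not. W3 caps TBL at 1.5 × ULN, and W1, C and R3 require that TBL is not elevated. Only ALT/AST lacks a ceiling throughout; for TBL, only W2 lacks one.
- *That one site would keep dosing while another stops for good.* In (a), (b) and (d) both bullets stop dosing at first. Continued dosing arises only in (c), and only where values are not trending upward.
- *That the hepatotoxicity rates in Table 3 (35.0% overall, 11.5% Grade 3 or higher, of 643 patients) measure the problem.* They are pooled AE rates across savolitinib studies. The documents give no frequency for patients in the overlap zones.
- *That the comparison between arms is biased.* Both arms receive savolitinib under the same rules and safety is summarised descriptively. No between-arm bias is shown.

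What remains is a drafting contradiction in a liver-safety rule that is still being applied.

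**What to change.** The sponsor's clinical team should reconcile the bullets of Appendix I 3.2.1 so that each ALT/AST and TBL combination, for first and for recurrent events, maps to one action and one set of resumption terms. This can be done with non-overlapping limits or an explicit order of precedence. The redraft should also state how the discontinue bullet that follows a hold (D2) relates to the withhold bullets. Which action applies in each range is a clinical decision, and this review proposes none.

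The cost is redrafting one appendix section, for instance as a table, through a protocol amendment. No analysis has to change.

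### Appendix I 3.2.1: the hold branch for ALT/AST > 3 × ULN with TBL > 1 to 1.5 × ULN restarts every unrecovered patient at a reduced dose, with no recovery floor, discontinue outcome or LFT schedule

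*Supplement*

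**What the plan says.** Appendix I 3.2.1 gives the savolitinib rules for drug-related liver toxicity. The branch at issue opens "Withhold dosing if ALT or AST > 3 × ULN and concurrent TBL > 1 × ULN to 1.5 × ULN", with LFTs repeated twice a week for one week. It then has two outcomes:

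- "If both ALT/AST and TBL improved to normal range (< Grade 1) or baseline in one week": restart at the same dose, with LFTs twice a week for 6 weeks.
- All other patients: "If not, resume at reduced dose". Nothing follows.

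The neighbouring branches are built differently. With TBL > 1.5 × ULN the rule is "If both ALT/AST and TBL improved to Grade 1 or baseline in one week, resume at reduced dose", with LFTs twice a week for 6 weeks, and discontinuation otherwise. With no TBL elevation it is "Continue dosing if ALT or AST > 3 × ULN without TBL elevation above baseline or ULN, repeat LFT testing every week". That branch holds only on a rising trend ("If ALT or AST trending upward, withhold dosing and repeat LFT twice a week for one week"), and it discontinues if Grade 1 or baseline is not reached within two weeks.

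Outside these branches, routine LFTs are weekly for the first 10 weeks and then on Day 1 of each 28-day cycle (Section 1.3, Table 1, footnote h). At most two savolitinib dose reductions are allowed (Appendix I 3.1, Table I5).

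**The concern.** The second outcome puts two different patients together: one who is nearly normal at one week and one whose values have not moved. For the first, a reduced-dose restart is sensible and only the LFT frequency is missing. For the second, the sub-bullet says restart while the parent bullet's trigger is still met and says hold. The text does not rank the two instructions, so sites may act differently on the same values.

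Patient safety is what is at stake. A site that follows the line re-exposes a patient whose transaminases and bilirubin are both still raised. Restart has its own hazard, because Appendix I 3.3 reports that acute hypersensitivity, including anaphylaxis, was seen mostly when savolitinib was restarted. Liver events are common with this drug: Table 3 (Section 2.3.1) gives hepatotoxicity in 35.0% of patients in the savolitinib database and Grade 3 or higher in 11.5%. The documents do not say how many patients reach this branch.

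**Working it through.** The plan states no figure to reproduce. The check reads the rules as a decision table and then counts LFTs.

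**1. The five hold branches of I 3.2.1, at the point where recovery is missed**

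| Hold branch | Recovery required | If missed |
|---|---|---|
| ALT/AST > 5 × ULN for > 2 weeks, or 8 × ULN, no TBL elevation | Grade 1 or baseline, one week | Discontinue |
| > 3 × ULN, TBL > 1.5 × ULN | Grade 1 or baseline, one week | Discontinue |
| > 3 × ULN, TBL > 1 to 1.5 × ULN | Normal range or baseline, one week (for same dose) | **Resume at reduced dose** |
| > 3 × ULN, no TBL elevation, rising | Grade 1 or baseline, up to two weeks | Discontinue |
| Recurrent > 3 × ULN, no TBL elevation | Grade 1 or baseline, one week | Discontinue |

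Four of five discontinue. The branches contain 1 + 1 + 2 + 2 + 1 = 7 resume steps. Six state an LFT schedule for the following 6 weeks; this one does not.

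**2. Which unrecovered patients does another rule catch?**

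Take one-week values on a grid (ALT 0.5 to 10 × ULN in steps of 0.5; TBL 0.5 to 3 × ULN in steps of 0.25), with no symptoms and a normal INR.

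- Still meeting the trigger (ALT > 3, TBL > 1 to 1.5): 14 ALT values × 2 TBL values = 28 states, all sent to restart.
- ALT > 5 with raised TBL, caught by the separate discontinue rule: 10 × 2 = 20.
- Caught by no discontinue rule: 28 − 20 = 8, that is ALT 3.5 to 5 and TBL 1.25 to 1.5 × ULN.

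Example: ALT 4 × ULN and TBL 1.25 × ULN, unchanged at one week. The sub-bullet says restart; the trigger says hold.

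The grid shows where the gap lies, not how often it occurs. With listed symptoms or INR > 1.5, the patient is discontinued under other rules.

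**3. Does the baseline alternative remove the conflict?** No. Inclusion criterion 11 (Section 5.1) admits ALT and AST ≤ 2.5 × ULN with TBL ≤ ULN, or TBL up to 1.5 × ULN with ALT and AST ≤ ULN. No eligible baseline meets the trigger.

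**4. Recurrence.** The three rules that name recurrence cover > 5 × ULN; "Discontinue for recurrent ALT or AST > 3 × ULN and TBL > 1.5 × ULN"; and "Withhold dosing for recurrent ALT or AST > 3 × ULN without TBL elevation above baseline or ULN". None names > 3 to 5 × ULN with TBL > 1 to 1.5 × ULN. The base bullet is not limited to a first episode, so a recurrence is held again and then meets the same restart line. With two reductions permitted, that allows at most two reduced-dose restarts.

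**5. LFTs in the 6 weeks (42 days) after restart**

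- Fully recovered patient, same bullet: 2 × 6 = 12.
- Under the disputed line, ALT/AST ≤ 3 × ULN: routine schedule only. This gives 6 if the window lies within week 10, and 42/28 = 1.5 (so 1 to 2) if it lies after. A window that straddles week 10 falls between: restart at Day 49 gives about 4 (weeks 8, 9 and 10, and Cycle 4 Day 1).
- ALT/AST > 3 × ULN with TBL no longer raised: the next bullet applies, weekly, so 6.
- Both still in the trigger band: not determinable, because the text supports both restart and renewed hold.

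**The case against.** The strongest reply is that no site is obliged to dose such a patient. Appendix I 3.1 lets the treating physician hold or reduce as clinically indicated, Section 6.6 leaves dose changes to the investigator, and Section 7.1 allows discontinuation for adverse events. The sponsor must be told once ALT or AST reaches 3 × ULN (Appendix E 3). Study-physician approval is needed to restart after an interruption in the first 6 weeks for savolitinib-related toxicity (Appendix I 3.3). This stands, and it means a reader should not infer that the protocol compels unsafe dosing. But none of these provisions sets a recovery floor, and a careful investigator stays safe only by departing from the written line.

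A second reply is that the line was meant for patients who have improved but are not yet normal, with the hold trigger still governing the rest. That may well be the intent, and part (a) of the fix adopts it. The text does not say so.

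Three stronger readings are tempting, and the documents do not support them:

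- *Raised bilirubin is treated more leniently than normal bilirubin.* This is true only at the non-recovery step. Earlier the branch is stricter: it holds at once, asks for normal values before same-dose restart, and tests twice weekly rather than weekly. The normal-bilirubin patients who discontinue were held because their values were rising, so the comparison is not like for like.
- *Recurrence in this band is uncontrolled.* The base bullet applies again and reductions stop at two. A note under Table I1 also discontinues patients already at the lowest dose.
- *The general Grade 3 rule in Table I1 shows what should happen here.* That table excludes toxicities with their own guideline, and the documents do not give the grade of this band.

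**Conclusion.** The point holds as a narrow safety defect in current, unredacted text. For asymptomatic patients still at ALT/AST > 3 to 5 × ULN with TBL > 1 to 1.5 × ULN after one week, the branch's restart instruction conflicts with its own hold trigger, and no discontinue rule covers them. All patients under the line also lack a restart-specific LFT frequency. It would be too strong to say that monitoring is absent, since routine LFTs continue, though only once per cycle after week 10.

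The conclusion assumes no listed symptoms, INR not raised, and eligibility values as in criterion 11. Recruitment has been terminated, but treatment continues, including after the final data cut-off (Sections 4.1.4 and 6.7), so the line still governs patients on savolitinib. It should be fixed. It changes no efficacy estimate, and the number of patients affected cannot be derived from the documents.

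**What to change.** Replace the single line with two:

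(a) If ALT/AST and TBL have recovered to Grade 1 or baseline but do not meet the same-dose criterion, resume at a reduced dose with LFTs twice a week for 6 weeks.

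(b) Otherwise do not restart. Keep holding, and discontinue if Grade 1 or baseline is not reached within a limit set by the sponsor's hepatic safety group: one week, as in the TBL > 1.5 × ULN branch, or two, as in the branch without TBL elevation. The choice is clinical and should weigh the restart hypersensitivity described in I 3.3.

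State that the same rule applies if this band recurs.

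The cost is a correction to Appendix I and a site communication. Extra local LFTs per restart under (a), against the routine schedule, are 12 − 6 = 6 within week 10, 12 − 4 = about 8 in the straddling example, and 12 − 2 = 10 to 12 − 1 = 11 afterwards. A few slow-recovering patients stop savolitinib earlier. In the savolitinib plus placebo arm before unblinding, stopping leaves placebo alone until progression permits cross-over (Sections 4.1.2 and 6.3). That should be weighed when the limit in (b) is set.
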